## 1. Abstract

Approximately 50-80% of patients who are considered high-risk or unfavorable intermediate-risk experience recurrent disease after being treated with definitive radical prostatectomy, often because of undetected extraprostatic metastatic spread. In addition, there is increasing evidence that performing radical prostatectomy in patients with high-risk disease or locally advanced disease is feasible and has potential benefit in terms of local control, overall survival, and quality of life [1-3]. Thus, improved imaging approaches for early detection of occult metastatic prostate cancer at the time of presentation could inform a directed treatment approach that would significantly improve patient outcome, including use of extended lymphadenectomy as well as postoperative radiation therapy planning.

Amino acid transport is up-regulated in prostate and other cancers. *Anti*-1-amino-3-[18F]fluorocyclobutyl-1carboxylic acid (FACBC) is a synthetic amino acid analog positron emission tomography (PET) radiotracer that has demonstrated promising results in the staging and restaging of prostate carcinoma, with high positive predictive value (PPV) in the identification of extraprostatic malignancy [4, 5]. Most of the prior studies of FACBC were in post-primary treatment recurrence, and this proposed trial will be the first comprehensive study to evaluate FACBC PET in detecting occult metastatic disease at initial diagnosis in patients with negative or equivocal conventional imaging with the objective of developing a more effective primary treatment plan.

The goal of this study is to determine if FACBC PET will detect significant occult metastatic disease in patients with high risk or unfavorable intermediate-risk primary prostate carcinoma who have negative or equivocal conventional imaging such as CT, MR and bone scan. In addition, amino acid regulation has been implicated in mTOR pathway signaling; therefore, we believe that FACBC may also play a complementary role with other biomarkers of aggressive or metastatic disease. Therefore, a secondary goal is to leverage the utility of FACBC as a biomarker of the upregulation of amino acid transport and to correlate FACBC uptake parameters with tissue RNA signatures of prostate cancer, and levels of novel serum and urine biomarkers (urine RNA and serum phi) as an adjunct to another ongoing study.

Our hypothesis is that FACBC PET imaging will detect occult metastatic prostate cancer at the time of presentation, especially nodal disease, in patients with newly diagnosed high risk or unfavorable intermediaterisk primary prostate cancer who have negative or equivocal conventional imaging. In addition, we hypothesize that FACBC as an imaging biomarker may play a complementary role to tissue RNA signatures of prostate cancer, as well as urine RNA and serum phi.

## 2. Background and Significance:

Most patients with prostate cancer present with clinically localized disease, yet after curative radical prostatectomy, over 30-50% of patients eventually present with biochemical failure and recurrence [6-8]. This is especially so in patients with high or very high risk prostate cancer in which failure rates may approach or exceed 50% [8-10]. While this higher failure rate is in part due to the biologic aggressiveness of disease, it is also likely that at the time of the initial treatment that metastatic disease was present but not appreciated. Despite advances in surgery, cryosurgery and radiation therapy of localized and hormonal treatment of extra-

prostatic disease, nearly all of prostate cancer deaths result from progressive metastatic disease. Thus, the presence or absence of extra-prostatic disease will change the therapeutic approach [8]. Imaging is central to the differentiation of prostatic from extraprostatic disease. In addition, with locoregional spread or even instances of metastatic disease, radical prostatectomy may still have benefit in regards to general health-related quality-of-life (HRQOL) and overall survival (OS) in this population [11]. Imaging may then play an even greater role in formulating individualized therapy plans.

Conventional imaging such as routine CT and MR has demonstrated relatively poor performance in the staging of high risk prostate cancer especially in terms of locoregional nodal spread and distant disease [12-16]. While FDG PET has been useful in patients with more aggressive castration resistant disease it also has suboptimal performance in the routine staging of patients with prostate cancer [17, 18]. FDG-PET is not accurate in the differentiation of cancer from inflammation, and generates suboptimal images in the pelvis where small lesions can be masked by the accumulation of FDG metabolites from urine accumulation in the bladder [17]. Other molecular imaging techniques such as the FDA approved Indium-capromab-pendetide radiotracer (ProstaScint) also have reported poor diagnostic performance [19-23]. Though newer PSMA ligands are promising, they are still early in their translation to routine clinical use [24].

Recent studies suggest that utilizing more advanced imaging such acetate and choline PET has the potential to improve early detection of occult metastatic prostate cancer of presumed locally confined primary and recurrent prostate carcinoma. Though there is suboptimal sensitivity for microscopic disease, added value has been described in higher risk prostate cancer to improve staging, especially in the detection of distant disease [25-30]. Schiavina has reported that while not sensitive enough to replace pelvic nodal dissection, imaging with choline PET demonstrated better diagnostic performance than clinical nomograms [31]. Yet, the isoform of the choline PET radiotracer that is available in the United States is based on carbon-11, which has a 20 minute half-life and is impractical without an on-site cyclotron. Though fluorocholine (FCH) with a longer half-life is available outside of the United States, intellectual property issues will limit its availability in the US until 2021. In addition, FCH has high bladder excretion which may be a limiting factor in image interpretation.

Amino acids are involved in a variety of biologic processes including protein synthesis, and amino acid transport is up-regulated in many neoplasms [32-35]. Consequently, radiolabeled amino acids, both natural and synthetic, have been utilized for oncologic molecular imaging. FACBC is an investigational synthetic non-metabolized amino acid analogue positron emission tomography (PET) radiotracer [4, 5, 36-43]. Transport is primarily mediated by sodium dependent amino acid transporters, specifically system ASC, with contribution by sodium independent system L [44, 45]. FACBC PET has been studied at multiple centers, primarily in the restaging of recurrent prostate carcinoma where it has demonstrated significantly better diagnostic performance than conventional imaging [4, 5, 39, 46, 47].

FACBC has characteristics that are advantageous in the imaging of prostate carcinoma including little renal excretion, and longer half-life of the fluorine-18 radioisotope. Most importantly, FACBC is FDA approved for recurrent prostate cancer detection. Thus, FACBC is an ideal PET radiotracer candidate to conduct a study determining if advanced molecular imaging provides significant value in the early detection of occult metastatic prostate cancer in high risk or unfavorable intermediate-risk patients before radical prostatectomy who have negative or equivocal conventional imaging, with the goal of informing a targeted treatment approach including extended pelvic nodal dissection and potentially postoperative radiotherapy and/or systemic therapy.

## 3. Objectives

## Primary Aim- To validate FACBC as an early indicator of occult metastatic disease among high risk or unfavorable intermediate-risk prostate cancer patients with presumed localized disease.

After completion of FACBC PET, detection rate for extraprostatic disease will be determined. In addition, after surgery and review of histology, correlation will be made to histologic findings for extraprostatic disease, as well as definitive skeletal imaging to determine diagnostic performance as a secondary analysis noted in the statistical analysis plan. Reference standards as to ground truth for extraprostatic disease will be established with histologic analysis of nodes harvested in extended nodal dissections, extrapelvic and/or skeletal biopsy and/or correlation with definitive imaging findings. Thus, for this aim: 1) positivity rate will be calculated for

FACBC PET for extraprostatic disease as the primary analysis; 2) diagnostic performance of FACBC in the detection of extraprostatic disease as confirmed with histology and/or correlative imaging will be determined as a secondary analysis.

## Secondary Aim- to evaluate the correlation of FACBC uptake in the prostate with presence of FACBCdetected metastasis.

With data obtained from the trial we will correlate uptake within known tumor in the prostate to the frequency of FACBC extraprostatic positivity. We will use various indices such as SUVmax, SUVpeak, SUVmean, total lesion activity, and retention indices of the primary tumor to determine if degree of uptake and uptake characteristics of FACBC PET as an imaging biomarker in itself indicate the propensity of the primary prostate cancer to metastasize as correlated with the reference standards of this trial.

# Exploratory Aim- to evaluate tissue RNA signatures of prostate cancer, as well as urine RNA and serum phi parameters that are associated with higher rate of FACBC positivity in this cohort.

Urine, tissue and serum samples will be obtained from all study participants for urine and tissue RNA, and serum Phi parameters through the Prostate Satellite Tissue Bank (IRB 00045859). With data obtained through the trial and in conjunction with other ongoing studies:

1) We will correlate tissue RNA signatures of prostate cancer, urine RNA and serum phi parameters with the detection rate of FACBC studies for extraprostatic disease.

2) We will also correlate FACBC uptake parameters within the prostate/primary tumor (such as but not limited to SUVmax, SUVpeak, SUVmean, total lesion activity, and retention indices as available) with tissue RNA signatures of prostate cancer, as well as urine RNA and serum phi parameters.

3) We will therefore determine if FACBC PET may be used as an adjunct imaging biomarker in combination with the novel tissue RNA signatures of aggressive prostate cancer, as well as urine RNA and serum phi biomarkers in the detection of more aggressive or metastatic disease.

4) We will also, at a later time point, correlate uptake within the prostate itself to pathology from Emory standard histologic processing, likely on a sextant basis. Specifically, we will correlate presence or absence of tumor, inflammation, and BPH with uptake parameters.

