For Aim 3, we will evaluate the association of the tissue RNA signatures of prostate cancer as well as urine and serum biomarkers with the rate of FACBC positivity using standard associative statistical tools including logistic regression and ANOVA as appropriate. Finally we will correlate FACBC uptake parameters in the primary prostate tumor to the tissue RNA signatures of aggressive prostate cancer and urine and serum biomarkers using Spearman's correlation coefficients.

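### The planned FACBC-versus-biomarker associations cannot show whether FACBC adds to tissue RNA, urine RNA and phi; exploratory item 3 needs a joint model against reference-standard disease, or a weaker conclusion

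*Combined protocol and SAP*

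**What the plan says.** The hypothesis in Section 1 reads: "FACBC as an imaging biomarker may play a complementary role to tissue RNA signatures of prostate cancer", and it names the urine and serum markers too. The Exploratory Aim in Section 3 approaches this in steps:

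- Item 1 relates the tissue signatures, "urine RNA and serum phi parameters with the detection rate of FACBC studies for extraprostatic disease".
- Item 2 reads "We will also correlate FACBC uptake parameters within the prostate/primary tumor" and sets that uptake against the same RNA and phi markers.
- Item 3 draws the conclusion, presented as following from the first two. The trial will "determine if FACBC PET may be used as an adjunct imaging biomarker in combination with the novel tissue RNA signatures" and the other markers. The stated target is use "in the detection of more aggressive or metastatic disease".

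Section 9, under Aim 3, supplies the methods. The first is to "evaluate the association of the tissue RNA signatures of prostate cancer as well as urine and serum biomarkers with the rate of FACBC positivity", by logistic regression or ANOVA. The second is a set of Spearman correlations between uptake in the primary tumour and the markers. Nothing further is planned for item 3.

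**The concern.** Item 3 is a question about detecting disease with a combination of tests. Answering it needs disease status as the outcome and both FACBC and the biomarkers as predictors. The planned analyses instead describe how FACBC and the biomarkers relate to each other, yet item 3 presents its conclusion as following from them.

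If the aim is carried out as written, a statement that FACBC is, or is not, a useful adjunct would rest on a quantity that does not determine the answer. Section 4 (Tissue and Data Management) says experience from this trial will be used to plan a multicenter trial, so such a statement could be carried forward.

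**Working it through.** **1. Is the needed analysis planned elsewhere?**

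| Planned analysis | Outcome | RNA/phi in the model? |
|---|---|---|
| Section 9, Aim 3, first part | FACBC positivity | Yes, but FACBC is the outcome |
| Section 9, Aim 3, second part | None (Spearman) | Pairwise with uptake only |
| Secondary Aim (Section 3; Section 9, Aim 2) | Extraprostatic detection | No |
| Section 9 cross-tabulation, sensitivity, kappa | Nodal dissection status | No |
| Exploratory item 4 | Sextant pathology in the prostate | No |

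No row has verified disease as outcome with FACBC and the markers as joint predictors.

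**2. The plan's own figures.** The exploratory aim has none. The Section 9 inputs reused below (prevalence 50%, sensitivity 40%, specificity 95%) reproduce the stated results: positivity 0.5×0.40 + 0.5×0.05 = 0.225, and PPV 0.20/0.225 = 0.889.

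**3. Same correlation, different answer.** Assumed: FACBC, marker and latent disease jointly normal; disease prevalence 50%; marker-disease correlation 0.5; FACBC-marker correlation 0.30.

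- FACBC-disease correlation 0.15: the FACBC coefficient given the marker is (0.15 − 0.30×0.5)/(1 − 0.09) = 0. AUC is 0.729 for the marker alone and 0.729 with FACBC.
- FACBC-disease correlation 0.50: the coefficient is (0.50 − 0.15)/0.91 = 0.385. AUC rises from 0.730 to 0.788.

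The FACBC-marker correlation is 0.30 in both cases.

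**4. The direction is not fixed either.** Take two binormal markers with separations d1 and d2 and within-group correlation r. The combined separation satisfies D² = (d1² + d2² − 2·r·d1·d2)/(1 − r²), and AUC = Φ(D/√2). At 50% prevalence the whole-cohort (Pearson) correlation is (r + d1·d2/4)/√[(1 + d1²/4)(1 + d2²/4)].

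- Equal markers, d1 = d2 = 1 (single AUC 0.760). For r = 0, 0.5, 0.8, 0.95 the combined AUC is 0.841, 0.793, 0.772, 0.763, while the whole-cohort correlation is 0.20, 0.60, 0.84, 0.96. The gain shrinks as correlation rises.
- Unequal markers, d1 = 1 and d2 = 0.2. At r = 0.2, D² = (1.04 − 0.08)/0.96 = 1, so there is no gain. At r = 0.8, D² = 0.72/0.36 = 2 and AUC is 0.841. At r = 0.95, D² = 0.66/0.0975 = 6.77 and AUC is 0.967. Over this range the gain grows with correlation.
- Equal markers, r = 0, d = 0.5, 1.0, 1.5. Whole-cohort correlation is 0.06, 0.20, 0.36 and combined AUC is 0.69, 0.84, 0.93. Both rise because both markers track disease.

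**5. Binary example with the protocol's FACBC inputs** and an assumed marker (sensitivity 60%, specificity 80%, so 40% marker-positive). The denominator of the binary correlation is √(0.225×0.775×0.4×0.6) = 0.2046.

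- Every FACBC-positive man is also marker-positive: joint positivity 0.225, correlation (0.225 − 0.09)/0.2046 = 0.66. Calling either test positive gains no sensitivity over the marker.
- Independent given disease: joint positivity 0.5×0.24 + 0.5×0.01 = 0.125, correlation (0.125 − 0.09)/0.2046 = 0.17. Sensitivity gains 16 points (60% to 76%) and specificity falls from 80% to 76%.

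**6. Could a joint model work at this size?** A likelihood-ratio test for adding FACBC to the marker was simulated in the two settings of step 3. At N = 88 and 50% prevalence it rejects about 0.90 of the time with a real gain and 0.07 without. At 30% prevalence (assumed) the figures are about 0.83 and 0.06. With 70 men at 30% they are about 0.76 and 0.06. These runs assume disease status is known without error.

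**The case against.** **The aim is exploratory and unpowered.** This stands as a limit on weight. It does not make an association into an estimate of added value.

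**Logistic regression could be multivariable.** It could, but the stated outcome is FACBC positivity. With FACBC on the left-hand side, its increment over the markers for detecting disease cannot be estimated.

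**The work is tied to other ongoing studies.** Sections 1 and 3 say so, and marker-versus-disease analyses may sit there. But no joint analysis is described, and item 3 draws its conclusion in this protocol.

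**A joint model has its own bias.** This is the strongest objection and it stands. FACBC findings may extend the dissection (Section 4, Standard of Care Procedures), may lead to biopsy of abnormal sites, and guide dissection and labelling (Histologic Assessment). Section 9 concedes that nodal dissection may miss substantial disease. Disease may therefore be found more often in FACBC-positive men because they were FACBC-positive. Assume N = 88, prevalence 50%, and an uninformative FACBC positive in 22.5%. If 60% of disease is found in FACBC-negative men and 75% or 90% in FACBC-positive men, the likelihood-ratio test rejects about 10% or 25% of the time, against about 5 to 6% with equal detection. The remedy must deal with this.

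**Two stronger readings are tempting and fail.** A reader might infer that the planned correlations systematically run against the complementarity hypothesis, since overlap suggests redundancy. Step 4 shows this depends on marker strengths and on whether correlation is taken within disease groups or, as planned, over the whole cohort. A reader might also infer that a strong correlation would be counted as success. The documents give no threshold, direction or decision rule for item 3.

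**Conclusion.** The point holds in this form: the two planned analyses do not identify the added value that item 3 says will be determined. The gap is in the choice of outcome and model, and it follows from the text without any numerical assumption. The size of any error cannot be derived from the documents. In the illustrations one correlation (0.30) is compatible with an AUC gain of zero or about 0.06, but the marker accuracies, correlations and 30% prevalence behind the illustrations are assumed. The consequence is confined to the item 3 conclusion and the complementarity hypothesis. The primary positivity analysis and the secondary analyses are unaffected.

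**What to change.** Add one exploratory nested comparison to the Aim 3 text of Section 9:

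1. **Outcome:** extraprostatic disease by the reference standard in Section 3.
2. **Models:** logistic regression on a single prespecified biomarker score, then the same model plus the FACBC result or one prespecified uptake measure.
3. **Report:** the likelihood-ratio test, and the optimism-corrected change in AUC with a bootstrap interval.
4. **Stated limitation:** verification is incomplete and partly FACBC-directed, which favours FACBC.
5. **Sensitivity analysis:** only men who had the standard nodal template, counting only template packets and excluding extra sites sampled because of FACBC.

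Keep the association and Spearman analyses as descriptive. Reword item 3 so that they support a statement of association only, and any adjunct statement is exploratory and rests on the joint model. If the joint model is not wanted, item 3 should claim association and no more.

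The cost is SAP wording and a few models on samples and reference data already planned. Intervals will be wide and some men will lack verified status. The template analysis speaks only to nodal disease within the template, and some verification bias will remain because FACBC reads also guide the dissection itself.

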## 4. Study Design

We will undertake a clinical trial with 88 patients who have been diagnosed with primary prostate carcinoma who are considered at least unfavorable intermediate-risk (Grade Group 2 (Gleason score 3+4) with either PSA 10-<20 or clinical stage T2b-c, OR Grade Group 3 (Gleason 4+3) with PSA < 20) or high risk per standard guidelines (clinical T3a, or Gleason score 8-10, or PSA greater than 20 ng/ml; and/or recurrence probability of  $\geq$ 50%) as per clinical assessment, without definitive findings of systemic metastasis on conventional imaging, and who are candidates for potentially curable radical prostatectomy and extended pelvic nodal dissection. We will employ the Kattan nomograms and other standard instruments as appropriate in making this determination [48]. Subsequently, patients will undergo whole body FACBC PET-CT. Typically patients will then undergo radical prostatectomy and extended nodal dissection, but if disease is detected preoperatively outside of the prostate, this will inform a discussion between the surgeon and patient as to an individualized treatment plan which may include targeted nodal dissection and use of postoperative radiotherapy and/or systemic therapy. Primary analysis will be centered on detection of occult extraprostatic disease by FACBC PET in high or very high-risk patients without definitive findings of systemic metastasis on conventional imaging. While the primary endpoint will be FACBC PET occult extraprostatic disease detection, as a secondary analysis we will crosstabulate the agreement between FACBC classifications versus extraprostatic disease status as identified by extended pelvic nodal dissection and other extraprostatic truth verification. Patients will also be followed for long-term outcome, but that is beyond the scope of this current trial.

**FACBC radiolabeling:** Production will be accomplished by the GE FastLab cassette system. Alternatively by automated synthesis developed by [name] and [name] [49]. We have prepared greater than 200 batch productions for tumor imaging in volunteer subjects. Imaging will be performed under the IND held by [name] and FDA mandated monitoring will be completed.

## Standard of Care Procedures

- 1. Conventional imaging: Prior to enrolment in this study, all patients will undergo standard of care preoperative bone scan and/or NaF PET, as well as nodal staging with diagnostic CT and/or MR per institutional standards. The official report is an important part of the initial evaluation and will serve as the basis for recording findings of extraprostatic disease since this will duplicate standard practice. Equivocal findings and/or non-definitive findings of systemic metastasis will be considered as negative for extraprostatic disease since management is typically not changed unless definitive radiologic findings are evident. The interpreter of the conventional imaging will have no access to FACBC imaging (and typically will be performed before FACBC). It is anticipated that all the conventional imaging will be reimbursed by third party payers.
- 2. Radical Prostatectomy and Extended Lymph node dissections: Patients will undergo standard of care radical prostatectomy and extended or super-extended pelvic node dissection. The surgical plan will generally involve nodal dissection of right and left obturator, right and left external iliac, right and left common iliac, right and left pre-sciatic, and central pre-sacral with optional para-aortic and para-caval regions subject to clinical exigencies. Each group of nodes will be removed as a packet, labeled separately and sent to pathology for routine histopathologic examination. If either conventional imaging or the FACBC scan demonstrates potential other pelvic or extrapelvic nodal disease, the surgeon may choose to extend the nodal dissection to other sites. If this is done, the additional nodes will be labeled to indicate the site and they will be also be submitted for pathology review. It is noted that some patients with extrapelvic disease may still undergo surgery after a discussion between patient and surgeon as to risks, advantages, and disadvantages since there is solid evidence that patients may still benefit from this approach [1-3, 11]. Burden of disease will likely be an important factor in this decision. In addition, since patient safety is paramount, an individual patient may have surgery stopped or altered due to clinical judgement, which will modify nodal basins sampled.

After the FACBC scan described below, and before surgery the diagnostic imager and the surgeon will communicate to review findings and to ensure consistency in correlation of findings to nodal packet nomenclature. In addition, patients with abnormal though non-definitive findings on conventional imaging and/or abnormal and/or equivocal and/or discrepant on FACBC PET-CT in extraprostatic or especially extrapelvic locations may also have those sites sampled as clinically appropriate through a combination of percutaneous image guided needle biopsy and/or laparoscopic techniques.

3. Serum, urine, and tissue samples will be collected for RNA and other genomic analysis.

